5.2. Patient and Study Completion

The study is planned to enroll ~15 patients, with ~5 to 10 patients aged >12 years, and up to 10 patients between 6 and 12 years.

A patient is considered to have completed the study if he/she has either:

- Receives the last planned setmelanotide dose at Week 16 (Visit 6), meets the primary endpoint, and elects to enroll in a separate extension study, Rhythm Study RM-493-022, under which auspices the patient will continue to receive setmelanotide.

- Receives the last planned setmelanotide dose at Week 16 (Week 6) and completes the EOS Visit (Visit 7) for a final safety review under the auspices of the current study.

[figure not shown]
Patients who discontinue before completing the 16-week treatment period are to attend a Treatment Discontinuation visit within 7 days (± 4 days) after the last setmelanotide dose for final study assessments.

The end of the study is defined as the date of the last visit of the last patient under the auspices of the current study.

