**Table 1 Analysis Visit Windows**

Analysis Visit	Target Study Day	Analysis Visit Window
(Intentionally left blank)	-56 - -1	<1*
Baseline	1	1
Week 4	29	2 - 43
Week 8	57	44 – 71
Week 12	85	72 – 99
Week 16	113	100 - 127
Week 20	141	≥ 128

\*The exception to this windowing is the height assessment completed prior to Baseline, as height assessments are not completed at Baseline visit. Visit 1 height assessments should be included in the Baseline analysis visit window.

If two or more assessments (include both scheduled and unscheduled assessments) are available for the analysis visits, then all assessments will be included in data listings and the following rules will be applied for determining the values to be used for the summaries and analyses in tables:

- Efficacy assessments: the assessment taken closest to the target study day will be used for the summaries and analyses; if two visits are equally distant to the target study day, then the more recently occurring visit will be chosen (i.e. If the target study day was 01 JAN 2021 and Visit A occurred on 27 DEC 2020 and Visit B occurred on 06 JAN 2021 (both 5 days apart from the target study day), then Visit B will be chosen).

Safety by-visit summaries and analyses will use the nominal evaluation visit, as recorded on the eCRF. Both scheduled and unscheduled visits (including early termination visit) will be windowed based on the protocol-specified windows outlined in [Section 16.1](#). If two or more assessments (include both scheduled and unscheduled assessments) are available for the visits, then all assessments will be included in data listings and the following rules will be applied for determining the values to be used for the summaries and analyses in tables:

- Safety assessments, excluding clinical laboratory tests: the scheduled visit will be used over any unscheduled visits conducted within window; otherwise, the assessment taken closest to the target study day will be used for the summaries and analyses
- Clinical laboratory tests: the scheduled visit will be used over any unscheduled visits conducted within window; otherwise, the latest assessment will be used for the summaries and analyses.

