## 8.6 Physical and Skin Examination

Changes in sexual function (described in [Section 3.5.3](#)) will be summarized by visit, separately for males and females, using descriptive statistics. The number of patients that experienced a change in sexual function will also be summarized. Skin examination results (described in [Section 3.5.3](#)) at Visit 1 and Visit 6 be summarized by skin region using descriptive statistics. Results from the hyperpigmentation assessment will be summarized by visit descriptively, including the number of patients that experienced a hyperpigmentation or skin change event.

Physical and skin examination assessments will be presented by patient in data listings. The physical examination listing will show the date of examination, indicator examination was not done (if applicable), reason examination was not done, and Tanner Staging results (if applicable). A listing displaying the details of the changes in sexual function, duration of change, and frequency of changes will be created, separately for males and females. The skin examination listing will show the date of examination, indicator examination was not done (if applicable), reason examination was not done, skin region, result of exam, and any noted findings. A listing displaying the details of skin hyperpigmentation, changes in skin tone, development of new moles, changes in existing moles, and AE relatedness will be created.

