## 10.6 Electrocardiograms

The ECG measurements (described in [Section 3.5.4](#)) at Visit 2 (pre and post-dose), Visit 3, Visit 6, and the changes from pre-dose baseline will be summarized descriptively at each visit. In addition, a shift table will be created to show any change from pre-dose baseline to each visit in the overall ECG interpretation.

QTcF interval prolongation will be presented separately as well. The number and percentage of patients with a QTcF interval of >450 msec, >480 msec, and >500 msec will be summarized by visit, along with the number and percentage of patients with a change from pre-dose baseline in QTcF interval of 30 - < 60 msec and  $\geq 60$  msec.

All ECG results will be presented in a data listing. The listing will show the assessment date, ECG measurement, indicator ECG was not done (if applicable), reason ECG was not done (if applicable) ECG value, the change from baseline.

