## 16 Appendices

### 16.1 Schedule of Assessments

Table 1: Schedule of Activities

Study Period/Procedure	Screening	Study Treatment						EOS Visit	Treatment Discontinuation Visit
		V1	V2	-	V3 	V4	V5	V6 	
Clinic Visit Number	V1	V2	-	V3 	V4	V5	V6 	V7 	
Study Day	-56 to -14	1	15	29	57	85	113	141	
Visit Window (days)	-	-	+3d	± 4 d	± 4 d	± 4 d	± 4 d	± 4 d	± 4 d
Informed consent/assent 	X								
Inclusion/exclusion criteria review	X	X							
Medical history review	X								
Physical examination 	X	X		X	X	X	X	X	X
Comprehensive skin examination 	X						X		X
Fitzpatrick classification scale	X						X	X	X
Weight 	X	X		X	X	X	X	X	X
Waist circumference 	X	X		X	X	X	X	X	X
Height 	X			X	X	X	X	X	X
Body composition assessment by DXA 	X						X		X
Vital signs 	X	X		X	X	X	X	X	X
ECG (12-lead) 	X	X 		X 			X 		X
Pregnancy test 	X	X 		X	X 	X 	X 		X
Daily hunger questionnaires 	X				Daily				X
Global hunger assessment 		X 		X 	X 	X 	X 	X	X
PHQ-A or PHQ-9 	X	X 		X 	X 	X 	X 	X	X
C-SSRS 	X	X 		X 	X 	X 	X 	X	X
SF-12 or SF-10 	X	X 		X 			X 		X
IWQOL-Lite-CT 	X	X 		X 			X 		X

Study Period/Procedure	Screening	Study Treatment						EOS Visit	Treatment Discontinuation Visit
		V1	V2	-	V3 	V4	V5	V6 	
Clinic Visit Number	V1	V2	-	V3 	V4	V5	V6 	V7 	
Study Day	-56 to -14	1	15	29	57	85	113	141	
Visit Window (days)	-	-	+3d	± 4 d	± 4 d	± 4 d	± 4 d	± 4 d	
EQ-5D-5L or Y 	X	X 		X 			X 		X
Safety laboratory tests 	X	X		X 	X 	X 	X 	X	X
FSH*	X								
Injection site inspection 			X		X	X	X		X
Telephone call 				X					
Review of type of lesion on MRI 	X								
Study drug administration 				Daily dosing					
Dispense/Return study drug 			X		X	X	X		

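### SAP 4.2 gives two unreconciled visit rules for by-visit safety data, and on either one most or all ECG, skin-examination and PHQ results from discontinuation visits are left out of the summaries

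*SAP*

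**What the plan says.** SAP 4.2 states two rules for safety data in consecutive sentences below Table 1. The first is "Safety by-visit summaries and analyses will use the nominal evaluation visit, as recorded on the eCRF". The second is "Both scheduled and unscheduled visits (including early termination visit) will be windowed based on the protocol-specified windows outlined in" Section 16.1. Where several non-laboratory assessments compete for one visit, "the scheduled visit will be used over any unscheduled visits conducted within window; otherwise, the assessment taken closest to the target study day" is used. For laboratory tests the fallback is the latest assessment. No rule covers a safety assessment that lies outside every window.

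The schedule in SAP 16.1 sets ±4 days around Days 29, 57, 85, 113 and 141. It also has a separate "Treatment Discontinuation Visit" column with no target study day. ECG, comprehensive skin examination, PHQ, C-SSRS, vital signs and safety laboratory tests are all marked there. Protocol 5.2 ties that visit to the last dose: early stoppers "attend a Treatment Discontinuation visit within 7 days" of it, ±4 days.

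The output sections differ in which visits they name:
- SAP 10.6 summarizes ECG "at Visit 2 (pre and post-dose), Visit 3, Visit 6, and the changes" from pre-dose baseline, and gives QTcF categories by visit.
- SAP 8.6 has skin-examination results "at Visit 1 and Visit 6 be summarized by skin region using descriptive statistics".
- SAP 10.7.2 reports PHQ total score and its change from baseline to 16 weeks.
- SAP 10.4, 10.5 and 10.7.3 cover laboratory tests, vital signs and C-SSRS at each visit, with changes or shifts at the post-baseline visits.

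**The concern.** The efficacy windows in SAP Table 1 are contiguous from Day 2, so every early-termination weight or BMI has a place. The safety windows are not contiguous, and a visit dated from the last dose lands among them by chance. Two programmers could follow SAP 4.2 faithfully and produce different safety tables.

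Separately, the schedule collects ECG, skin and PHQ data at discontinuation, but the matching summary sections name visits that do not include it. The readable SAP text has no worst post-baseline summary that would bring these results back.

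Safety and tolerability is a secondary endpoint of this study. Some patients may stop for tolerability, and their last assessments are then of particular interest. QTcF outlier counts, skin-examination summaries and PHQ summaries that omit those assessments describe mainly the patients who stayed on drug.

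**Working it through.** The plan states no figure for unmatched visits, so there is none to reproduce.

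**Inputs**
- Targets: Days 29, 57, 85, 113 and 141, each ±4 days (SAP 16.1).
- Windows: Days 25-33, 53-61, 81-89, 109-117 and 137-145.
- Gaps: Days 2-24 (23 days), then 34-52, 62-80, 90-108 and 118-136 (19 days each).
- Discontinuation visit: 7 ±4 days after the last dose (Protocol 5.2), taken as 3 to 11 days.
- Assumption: all last-dose days and all offsets are equally likely. The documents give neither a dropout rate nor its timing.

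**Reading A: early-termination visits windowed strictly to Visits 3-7**

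Unmatched share = 1 − (visit days inside a window ÷ all equally likely visit days).

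| Case | In a window | Unmatched |
|---|---|---|
| Last dose Days 1-112, visit +3 to +11 (112 × 9 = 1008) | 321 | 687/1008 = 68.2% |
| Last dose Days 1-112, visit +7 | 36 of 112 | 76/112 = 67.9% |
| Last dose Days 1-112, visit +0 to +11 (112 × 12 = 1344) | 417 | 927/1344 = 69.0% |
| Visit +3 to +11, only visits before Day 109 | 243 of 909 | 666/909 = 73.3% |
| Visit +7, only visits before Day 109 (Days 8-108) | 27 of 101 | 74/101 = 73.3% |

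The difference between 68% and 73% comes from whether visits on or after Day 109 count, since many of those land in the Visit 6 window. If all stops fall within the first 28, 56 or 84 days, the +3 to +11 result is 69.0%, 68.5% or 68.3%. Cruder variants, with a uniform visit day over other ranges and the Day 15-18 call window counted or not, run from about 64% to 76%.

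**Reading B: the visit keeps its nominal Treatment Discontinuation label**

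Unmatched share is 0%. Vital signs, laboratory tests and C-SSRS are summarized at each visit, so the discontinuation visit can have its own row.

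**Outputs whose sections name visits**

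Under Reading B, a result labelled Treatment Discontinuation is not among the named visits, so all of these results are left out. Under Reading A, a result enters only if it lands in a named visit's window. For last dose Days 1-112 and visit +3 to +11:
- ECG (Visit 3 or Visit 6 window): 159 of 1008 enter, so 849/1008 = 84.2% do not. The share is 91.1% (828/909) with the Day 109 cut-off and 69.0% (174/252) if all stops occur by Day 28.
- Skin examination and Week 16 PHQ (Visit 6 window): 78 of 1008 enter, so 930/1008 = 92.3% do not. With the cut-off, none enters.

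**Contrast**

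Under the contiguous efficacy windows, 0 of the 111 days from Day 2 to Day 112 are unmatched.

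**The case against.** The strongest reply is that the SAP nowhere says an assessment outside the Visit 3-7 windows is dropped. The nominal-visit sentence comes first, the schedule lists the discontinuation visit as a visit of its own, and the first block of the window row in SAP 16.1 carries one more ±4-day entry than Visits 3-7 need. Read together, the visit has its own label and window. This stands. A reader might infer that about three in four discontinuation visits match nothing and vanish from all by-visit safety tables. The documents support that only as one reading, and only with uniform timing and the Day 109 cut-off.

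A reader might also infer that early stoppers' results survive only in listings, that each lost patient costs 6.7% (1 of about 15) of every safety denominator, or that the whole safety profile leans towards looking safer. None of these holds:
- Adverse event tables are not by visit, and Protocol Appendix 6 makes clinically significant laboratory, ECG and vital-sign abnormalities adverse events, apart from those tied to underlying disease.
- SAP 8.6 also counts patients with hyperpigmentation or skin-change events.
- Laboratory and C-SSRS shift denominators count only patients with values at that visit, and an early stopper's completed visits still contribute.

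The ECG, skin and PHQ omissions come from the visit lists in their own sections, not from SAP 4.2. That is correct, and it is why they remain under either reading. Table shells are a separate document and part of SAP 10.4 is redacted, so the absence of a worst-value row is established only for the readable text.

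Moving these visits into the Table 1 weeks would have a real drawback. With a half-life of about 10-12 hours (Protocol 3.2), a visit at least 3 days (72 hours) after the last dose is at least 72/12 = 6 half-lives off drug, and would be mixed with on-treatment values.

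**Conclusion.** The point holds in two parts. First, SAP 4.2 leaves open how discontinuation visits enter by-visit safety tables. The unmatched share is 68% to 73% if they are windowed strictly to Visits 3-7 with uniform timing, and 0% under a nominal label. Second, for ECG/QTcF, skin examination and PHQ the summaries as written omit all discontinuation results under the nominal label. Under strict windowing they omit most: 84% for ECG and 92% for skin and PHQ in the main case.

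The second part does not depend on which rule governs, though the strict-windowing percentages rest on uniform timing. The number of patients affected is unknown and, with about 15 planned, probably small. The effect is confined to those summaries and, on one reading, the other by-visit safety tables. This is a gap to close before the tables are produced, not evidence that the overall safety assessment is biased.

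**What to change.** In SAP 4.2, state that the Treatment Discontinuation visit is tabulated under its own nominal row and is not pooled into on-treatment weeks.

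In SAP 8.6, 10.4, 10.5, 10.6, 10.7.2 and 10.7.3, add an any-post-baseline (worst value) row based on every post-dose assessment, including discontinuation and unscheduled visits. It should cover skin findings, laboratory shifts, blood pressure and heart rate, QTcF thresholds and change categories, PHQ and C-SSRS. This row also picks up unscheduled results that lie between windows or are overridden by a scheduled value within one.

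The cost is SAP wording and one or two extra rows per table, with no new data or patients. The worst-value row mixes on-drug and shortly off-drug values, and a footnote should say so.

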### 4.3 Baseline Definitions

For all analyses, baseline will be defined as the most recent measurement prior to the first administration of study drug, including assessments done at the Screening visit (Visit 1),

Unscheduled visits conducted prior to study treatment, and pre-treatment assessments done at the Baseline visit (Visit 2).

In general, change from baseline ( $\Delta$ ) will be calculated as the value at a given time point,  $X$ , minus the baseline value:

$$\Delta = X \text{ Value} - \text{Baseline Value}$$

## 5 Analysis Populations

### 5.1 Full Analysis Set Population

The Full Analysis Set (FAS) population will include all patients who received at least 1 dose of setmelanotide and have baseline data.

### 5.2 Per-Protocol Population

The Per-Protocol Set (PP) population will include all patients in FAS without any major protocol violations that will result in exclusion of the patients from the analysis.

### 5.3 Safety Population

The Safety Analysis Set population will include all patients who received at least 1 dose of study drug.

## 6 Patient Disposition

The disposition of patients will be presented in total, including:

- Number of patients screened, including screen failures
- Number of patients enrolled into the study
- Number of patients who completed the study
- Number of patients who early withdrew/discontinued from the study
- Number of patients that continued onto the extension study (RM-493-022)
- Number of patients in the FAS population
- Number of patients in the PP population
- Number of patients in the Safety population

Specifically, the number and percentage of patients in each of the specified categories above will be presented. Percentages for the number of patients enrolled will be based on the number of patients screened; all other percentages will be based on the number of patients enrolled. The discontinuation reason as specified on the eCRFs will also be summarized by number and percent under 'Early withdrawals/discontinuations' section.

All patients' disposition information (date of study completion/discontinuation, reason for discontinuation, date of last dose, reason for treatment discontinuation, and COVID-19 impact) will be presented in a data listing. Inclusion/exclusion data will also be presented by patients in a data listing.

## 7 Protocol Deviations

A protocol deviation occurs when a patient deviates from the protocol procedures. Depending on the seriousness of the deviation, the patient might be excluded from the PP analysis. For this study, the protocol deviations that will exclude patients from PP are identified (but not limited to) in Table 2 below.

**Table 2 Protocol deviations**

Deviation
Any patient that does not have a body weight measurement at the primary endpoint visit (Visit 6)
Any patient that does not have an available screening or baseline body weight measurement
Any enrolled patient that reports an eligibility-related protocol deviation.
Any patient with prohibited concomitant treatments/procedures prior to Visit 6 considered to have a substantial impact on the primary efficacy outcome.
Any patient with a prohibited medical history, unstable medical history condition, or medical history condition that worsens prior to Visit 6 considered to have a substantial impact on the primary efficacy outcome.

All protocol deviations will be presented by patient in a data listing. Patients who are excluded from the PP population will also be presented in a data listing, along with their reason(s) for exclusion. Protocol deviation listings will be reviewed, and each patient will be classified as belonging to the per-protocol set or not. Exclusions from the per-protocol set will be identified and documented prior to database lock.

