7.4. Blinding

This is an open-label study; no blinding methods will be employed.

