# 9 Efficacy Analysis

The primary efficacy analysis will be analyzed based on the FAS population. A supportive analysis based on PP will be performed as needed. All secondary efficacy and exploratory efficacy endpoints will be analyzed based on the FAS population, unless otherwise specified below.

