### 9.1.1 Sensitivity Analysis of Primary Endpoint

To assess the robustness of the primary efficacy results, the following additional sensitivity analyses will be conducted:

- Analysis of proportion of patients who achieve at least 5% BMI reduction from baseline, at ~16 weeks of treatment with setmelanotide will be repeated on the PP population, as needed.

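### SAP Table 2 allows per-protocol exclusion for a worsening medical condition judged, unmasked, to affect the primary outcome, so membership of the per-protocol set can depend on outcome

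*SAP*

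**What the plan says.** SAP Section 7 defines its subject: "A protocol deviation occurs when a patient deviates from the protocol procedures". It then says that "the protocol deviations that will exclude patients from PP are identified (but not limited to) in Table 2 below". Table 2 has five rows. The last concerns medical history and has three limbs: a prohibited history, an unstable condition, and a "medical history condition that worsens prior to Visit 6 considered to have a substantial impact on the primary efficacy outcome". The row above it, on prohibited concomitant treatments and procedures, uses the same test of judged impact on the primary outcome.

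SAP 5.2 and Protocol 10.2 define the PP set as FAS patients without major protocol violations that lead to exclusion.

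On process, the text under Table 2 says that deviation listings are reviewed, that excluded patients are listed with their reasons, and that "Exclusions from the per-protocol set will be identified and documented prior to database lock". It does not say who reviews, against what threshold, or with which data hidden. Protocol 7.4 states: "This is an open-label study; no blinding methods will be employed".

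On use, SAP Section 9 says: "The primary efficacy analysis will be analyzed based on the FAS population". A PP analysis is supportive. SAP 9.1.1, whose stated purpose is to check the robustness of the primary result, has one bullet: the responder analysis "will be repeated on the PP population, as needed". SAP 11.1 adds multiple imputation as a further optional sensitivity analysis, with methods in 16.5.

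**The concern.** A per-protocol set should be defined by what was done to or by the patient, not by how the patient fared. A condition that worsens on treatment belongs to the second kind. Exclusion also turns on whether the worsening is thought to have affected efficacy, and nobody making that judgement is masked. Weight is taken at every clinic visit, and Visit 6 response decides who may be eligible for the extension study (Protocol 5.1), so response is known well before database lock.

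Two features widen the opening. The disease under study is not excluded from the conditions that can worsen, and Table 2 is expressly not exhaustive.

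What is at stake is the value of the robustness check. If patients who did badly can be taken out by judgement, a PP result that agrees with or improves on the FAS result says little about whether the FAS result is robust.

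**Working it through.** **Text side by side.** SAP Section 7 ties a deviation to protocol procedures, and SAP 5.2 ties PP exclusion to major violations. The first four rows of Table 2 concern missing weights, eligibility or prohibited treatment. The worsening limb of the fifth row describes neither a missed procedure nor a breach of a rule. It fits neither definition.

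**Inputs.** The test is exact binomial, one-sided at 0.05, with a null rate of 5% (SAP 9.1). The interval is a two-sided 90% Clopper-Pearson interval (SAP 9.1). Planned enrolment is approximately 15 (Protocol 5.1, SAP 3.2), with up to 10 + 10 = 20 in the power statement (SAP 3.4). The target response rate is 40% (SAP 3.4). The documents give no PP exclusion rate, so the number of non-responders removed, k, is an assumption throughout. There is therefore no plan figure for this point to reproduce. The ~90% power in SAP 3.4 concerns a different question and is not used here.

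**Effect on the estimate.** The PP rate is x/(n − k) for x responders. At the target rate with n = 15, x = 6:
- k = 0: 6/15 = 40.0% (90% CI 19.1 to 64.0%)
- k = 2: 6/13 = 46.2% (22.4 to 71.3%)
- k = 3: 6/12 = 50.0% (24.5 to 75.5%)

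**Effect on the test.** p = Σ C(m, j) 0.05^j 0.95^(m−j), summed over j from x to m, with m = n − k.

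| Before removal | p | k (assumed) | After removal | p |
|---|---|---|---|---|
| 3/15 | 0.0362 | none needed | – | – |
| 2/15 | 0.1710 | 7 | 2/8 | 0.0572 |
| 2/15 | 0.1710 | 8 | 2/7 | 0.0444 |
| 3/17 | 0.0503 | 1 | 3/16 | 0.0429 |
| 3/18 | 0.0581 | 2 | 3/16 | 0.0429 |
| 3/20 | 0.0755 | 4 | 3/16 | 0.0429 |

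For two responders the sum reduces to 1 − 0.95^m − 0.05m × 0.95^(m−1). At m = 7 that is 1 − 0.6983 − 0.2573 = 0.0444.

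At n = 15, three or more responders are already significant, and two become so only at m = 7. One responder gives 1 − 0.95^8 = 0.337 even at m = 8. So no PP decision changes for k = 1 to 7.

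**Worst-case type I error of the PP test** (true rate 5%, up to k non-responders removed):
- n = 15: 3.6% for k = 0 to 7, then 17.1% at k = 8
- n = 20: 1.6% for k = 0 to 3, then 7.6% from k = 4

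The one-patient change needs n = 17 and exactly three responders. At the 40% target rate that has probability C(17, 3) × 0.4³ × 0.6¹⁴ = 3.4%.

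**The case against.** The strongest reply is that this is a supportive analysis, run only if needed, with its exclusions fixed before lock and listed by patient with reasons. In a study of about 15, any reader can see who was dropped. That stands as transparency. It does not mask the decision, because response is already known when the decision is made.

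Several stronger readings are tempting but not supported:

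- *The PP set is selected on outcome.* The rule requires a worsening condition, not non-response, and names no direction. A patient whose illness caused weight loss could be removed as a responder: 6/15 would become 5/14 = 35.7%. The text permits outcome-related selection; it does not prescribe it.
- *Any patient who gains weight meets the rule.* The condition must have an impact on the outcome, which points to a cause separate from the outcome. The gap is that hypothalamic obesity is not carved out.
- *A negative trial could be made positive.* The primary analysis is on the FAS, and no success rule uses the PP result.
- *There is no other sensitivity analysis.* Multiple imputation is named in SAP 11.1 and 16.5, though it is optional.

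A reader might also want a minimum-injection rule, since Table 2 has no dosing criterion. The documents give no threshold. In an open-label trial stopping injections may itself follow from seeing no benefit, so such a rule could bring back the same selection.

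**Conclusion.** The defect is real and limited. Table 2 classes a post-baseline medical event as a protocol deviation and makes exclusion depend on an unmasked judgement about efficacy, within an open-ended list. PP membership can therefore depend on outcome, which weakens the only analysis listed in SAP 9.1.1.

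The primary FAS result is unaffected. At about 15 patients the expected harm is an overstated PP response rate, about 6 percentage points if two non-responders are removed from 6/15, together with misplaced reassurance. A changed PP decision is unlikely at that size, since it would take eight removals from 2/15. With larger enrolment the PP test is more sensitive: one removal suffices at 3/17, two at 3/18 and four at 3/20. All these figures rest on an assumed number of removals, all of them non-responders.

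**What to change.** 1. In the medical-history row of Table 2, delete the limb on a condition that worsens before Visit 6. Keep the prohibited-history and unstable-condition limbs.
2. In SAP Section 7, delete the parenthesis that makes the list non-exhaustive.
3. State that PP status is assigned from listings that omit post-baseline weight, height and BMI. This should include the judgements of substantial impact that remain in the prohibited-treatment and medical-history rows. Keep the existing requirement to document exclusions before lock.
4. Describe any patient with a confounding illness individually in the study report.

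The cost is SAP wording and one set of restricted listings. The downside is that a patient with a truly confounding illness stays in the PP set and is handled by description. The change does not touch the first row of Table 2, which drops every patient without a Visit 6 weight. That is a separate route by which the PP set can become selective.
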